##### **4.2.3.1 Efficacy Endpoints**

Our secondary endpoints will be to estimate progression free survival (PFS) and overall survival (OS).

##### **4.2.3.2 Biomarker Research**

We will assess multiple biomarkers of interest through the collection of blood and tissue specimens through the following optional studies:

- A) Tissue specimen collection for biomarker analysis: Diagnostic and surgically resected tumor tissue will be acquired from the source used to establish the diagnosis of malignancy, including archival specimens stored in the Pathology Department and

residual fresh or fixed tissues banked in institutional tissue banks. Cytologic samples may also be included, though cell blocks are strongly preferred. The cell and tissue samples will be catalogued, then reviewed by a pathologist for malignant cell content and pathological analyses, and for correlative marker studies. The molecular marker analysis will include, among others, the analysis of protein expression, gene expression, copy number, mutations, and translocations, and micro-RNA expression abnormalities. The methodology to be used to examine molecular changes will be selected based on the characteristics of the sample collected (e.g. cells or tissue, archival or frozen). Immune markers of interest include but are not limited to the following:

*Inhibitory Markers (blocking T-cell activation):* PD-1, PD-L1, CTLA-4, BTLA, TIM3, LAG3

*Costimulatory Markers (promoting T-cell activation):* CD28, CD80, CD86, HLA-1, ICOS, ICOSL, 41BBL, 41BB

B) Serologies/Blood-Based Biomarkers – For evaluation of circulating immune biomarkers of interest including cytokines, measurements of T-cell activation, circulating tumor DNA (ctDNA) and exosome microRNAs. Three categories of specimens will be collected:

- A) EDTA Vacutainer (CAFs): 10 mL = 1 x 10 mL
- B) Streck CF-DNA BCT (ctDNA): 10 ml = 1 x 10 mL
- C) Sodium Heparin (immunoprofiling=immuno): 60 ml = 6 x 10 mL

All blood will be collected and processed by Thoracic Research Team according the institutional and laboratory standard operating procedures (SOPs).

Optional blood samples will be collected at the following timepoints:

- 1) Prior to RT (baseline): ctDNA, cytokine angiogenic factors (CAFs), immunoprofiling
- 2) After RT (+/- 3 days): CAF, immunoprofiling
- 3) After 2 cycles of immunotherapy (+/- 3 days): CAF, immunoprofiling
- 4) Progression/off study within 30 days of discontinuation or prior to starting next treatment: ctDNA, CAF, immunoprofiling methodology

## 4.3 Entry Criteria

### 4.3.1 Diagnosis/Condition for Entry into the Trial

Patients will have a diagnosis of malignant pleural mesothelioma and will not have undergone EPP as a component of their treatment.

### 4.3.2 Subject Inclusion Criteria

In order to be eligible for participation in this trial, the subject must:

1. Patients must have a histologic diagnosis of malignant pleural mesothelioma, with histologic diagnosis from the pleura or relevant lymph node stations, including mediastinal, hilar, or supraclavicular lymph nodes.
2. Be willing and able to provide written informed consent/assent for the trial.
3. Be  $\geq 18$  years of age on day of signing informed consent.
4. Have measurable or non-measurable disease per RECIST 1.1. However, note that patients in Cohort 1 that have undergone an R0 resection will be eligible for the trial.
5. Have a performance status of 0 or 1 on the ECOG Performance Scale.
6. Demonstrate adequate organ function as defined in Table 1, all screening labs should be performed within 10-15 days of treatment initiation.

Table 1 Adequate Organ Function Laboratory Values

System	Laboratory Value
Hematological	
Absolute neutrophil count (ANC)	$\geq 1,500 / \text{mcL}$
Platelets	$\geq 100,000 / \text{mcL}$
Hemoglobin	$\geq 9 \text{ g/dL}$ or $\geq 5.6 \text{ mmol/L}$ without transfusion or EPO dependency (within 7 days of assessment)
Renal	
Serum creatinine OR Measured or calculated a creatinine clearance (GFR can also be used in place of creatinine or CrCl)	$\leq 1.5 \times$ upper limit of normal (ULN) OR $\geq 60 \text{ mL/min}$ for subject with creatinine levels $> 1.5 \times$ institutional ULN
Hepatic	
Serum total bilirubin	$\leq 1.5 \times$ ULN OR Direct bilirubin $\leq$ ULN for subjects with total bilirubin levels $> 1.5 \text{ ULN}$
AST (SGOT) and ALT (SGPT)	$\leq 2.5 \times$ ULN OR $\leq 5 \times$ ULN for subjects with liver metastases
Albumin	$\geq 2.5 \text{ mg/dL}$
Coagulation	
International Normalized Ratio (INR) or Prothrombin Time (PT)	$\leq 1.5 \times$ ULN unless subject is receiving anticoagulant therapy as long as PT or PTT is within therapeutic range of intended use of anticoagulants
Activated Partial Thromboplastin Time (aPTT)	$\leq 1.5 \times$ ULN unless subject is receiving anticoagulant therapy as long as PT or PTT is within therapeutic range of intended use of anticoagulants

aCreatinine clearance should be calculated per institutional standard.

7. Female subject of childbearing potential should have a negative urine or serum pregnancy within 72 hours prior to receiving the first dose of study medication. If the urine test is positive or cannot be confirmed as negative, a serum pregnancy test will be required.
8. Female subjects of childbearing potential should be willing to use 2 methods of birth control or be surgically sterile, or abstain from heterosexual activity for the course of the study through 120 days after the last dose of study medication (Reference Section 5.7.2). Subjects of childbearing potential are those who have not been surgically sterilized or have not been free from menses for > 1 year.
9. Male subjects should agree to use an adequate method of contraception starting with the first dose of study therapy through 120 days after the last dose of study therapy.

**Additional Inclusion Criteria – Cohort 1 (Patients Receiving Hemithoracic Radiation Therapy)**

1. Patients must not have evidence of metastatic disease per PET/CT scan. Mediastinal lymph node involvement is acceptable.
2. Patients will have received at least 2 cycles of induction chemotherapy with pemetrexed/cisplatin or pemetrexed/carboplatin.
3. The following pulmonary function tests are required:
  - a.  $FEV_1 \geq 30\%$  of predicted postoperative (ppoFEV1, as if the patient underwent a pneumonectomy) based on the following formula using a quantitative perfusion scan: Predicted post-resection  $FEV_1 = FEV_1 \times \% \text{ perfusion to the uninvolved lung}$  from the quantitative perfusion report.
  - b.  $DLCO > 35\%$  predicted.
4. Patients must be assessed to be a suitable candidate for hemithoracic radiation therapy per the treating radiation oncologist. If the patient undergoes pleurectomy/decortication, they must initiate hemithoracic radiation therapy within 4 months of the surgery date. Patients that do not meet the dose constraints outlined below will be removed from the study prior to radiation therapy.

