Studies such as these have suggested that patients are optimally treated with lung sparing approaches. However, radiation therapy when the ipsilateral lung is intact, with or without surgery, presents unique issues. First, the presence of functional lung tissue on the same side as the target volume exposes the patient to the risk of radiation pneumonitis in this lung. Second, presuming that the ipsilateral lung is functional, patients can theoretically experience significant functional decline due to the difficulty in sparing this structure. Finally, if much of the ipsilateral lung is nonfunctional after RT, a “shunting” effect can occur whereby patients continue to perfuse to the ipsilateral lung, yet air exchange does not occur. For these reasons, hemithoracic radiation treatment with two functional lungs can paradoxically be more challenging than with only one lung intact.

[figure not shown]

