#### **4.4.4.4 – Radiation Dose Constraints – Both Cohorts**

*Required Dose Constraints* – Patients are required to meet the following dose constraints: 1) Normal Tissue Complication Probability (NTCP) of the lung <25%, calculated with the Lyman-Kutcher-Berman model [19]. 2) At least 93% of the contralateral lung must receive less than 20 Gy (V20<7%). 3) Maximum spinal cord dose of <50 Gy.

*Suggested Dose Constraints* – We suggest the following dose constraints: 1) At least 50% of heart receive less than 30 Gy, 2) At least 50% of the liver receive less than 30 Gy. 3) Mean dose to stomach (not PTV)<30 Gy, 4) Maximum bowel dose<55 Gy, 5) Kidney V18≤50%.

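### Two eligibility thresholds do not work as printed: the Cohort 1 FEV1 rule is always true when read literally, and the albumin limit in Table 1 carries a unit that lets every patient pass

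*Combined protocol and SAP*

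**What the plan says.** The Cohort 1 criteria in Section 4.3.2 introduce item 3 with "The following pulmonary function tests are required". Item 3a sets FEV1 at 30% or more "of predicted postoperative (ppoFEV1, as if the patient underwent a pneumonectomy) based on the following formula using a quantitative perfusion scan". The formula that follows gives predicted post-resection FEV1 as FEV1 multiplied by the percentage of perfusion going to the uninvolved lung. It does not say whether FEV1 is in litres or in percent of predicted normal. Item 3b, the next line, does give its reference: DLCO above 35% predicted.

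Table 1 in Section 4.3.2, which applies to both cohorts, requires albumin of at least 2.5 mg/dL. The same table requires hemoglobin of at least 9 g/dL. No other section restates the FEV1 rule or gives albumin another unit.

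The flow chart in Section 5.1 requires a quantitative perfusion scan at screening for Cohort 1 only.

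**The concern.** An eligibility threshold should be able to exclude someone. Item 3a, taken word for word, cannot, because its two sides are the same measurement with one side scaled down. A reader who notices this must choose a substitute rule, and the text does not settle which one.

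The criterion has a purpose in this protocol. Section 4.1 gives the reason for caution when the ipsilateral lung is intact: "patients can theoretically experience significant functional decline due to the difficulty in sparing this structure". It also describes continued perfusion of a lung that no longer exchanges air. Item 3a is the only entry criterion that uses the split of perfusion between the lungs. If it does not bind, or binds differently according to the reader, eligibility for a patient with low reserve cannot be audited against the protocol.

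The albumin line is simpler: with the printed unit, the limit lies far below any value a patient could have.

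**Working it through.** There is no sample size, power or error rate to reproduce. The check is algebra and a unit conversion.

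**FEV1, literal reading.** Let F be measured FEV1 and q the perfusion fraction of the uninvolved lung (0 < q ≤ 1), both as used in item 3a.

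- Definition: ppoFEV1 = F × q.
- Condition: F ≥ 0.30 × F × q. Dividing by F gives 1 ≥ 0.30q.
- At q = 1, the hardest case, F is 1/0.30 = 3.33 times the threshold. At smaller q the margin is wider.

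The condition holds for every patient, whether F is in litres or in percent predicted, because the unit cancels.

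**FEV1, the two other readings.** Here F is in percent of predicted normal.

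- Measured reading: F ≥ 30.
- ppoFEV1 reading: F × q ≥ 30.

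| F (% predicted) | q | ppoFEV1 = F × q | Literal threshold 0.30 × F × q | Literal | Measured F ≥ 30 | ppoFEV1 ≥ 30 |
|---|---|---|---|---|---|---|
| 84 | 0.50 | 42 | 12.6 | pass | pass | pass |
| 50 | 0.50 | 25 | 7.5 | pass | pass | fail |
| 40 | 0.55 | 22 | 6.6 | pass | pass | fail |
| 25 | 1.00 | 25 | 7.5 | pass | fail | fail |

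The patients are illustrative, except that 84% is the median baseline FEV1 which Section 4.1 reports for the institution's series of 22 patients.

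Under the ppoFEV1 reading, the lowest admissible F is 30/q: 30/0.50 = 60%, 30/0.60 = 50% and 30/0.80 = 37.5% predicted. Under the measured reading it is 30% whatever the perfusion. Under the literal reading there is no minimum.

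**Albumin.** 2.5 mg/dL ÷ 1000 = 0.0025 g/dL. An albumin of 1.0 g/dL is 1000 mg/dL, and 1000/2.5 = 400 times the printed limit. A value of 2.4 g/dL is 2400 mg/dL, or 960 times the limit. On a g/dL scale, both would fall below 2.5.

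**The case against.** The strongest reply is that nobody would apply the literal rule. The ppoFEV1 label, the pneumonectomy wording, the formula and the required scan make sense only if the perfusion-adjusted value is held against the 30%. Item 3b and Section 4.1 both express lung function in percent predicted. Likewise, a reader holding an albumin result in g/dL would probably take 2.5 to be on that scale. This carries weight: item 3a is better described as ambiguous than as certain to fail, and the albumin line looks like a unit slip. But neither is settled by the text, and eligibility should not depend on inference.

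Three stronger conclusions are tempting, and the documents do not support them.

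- A reader might infer that patients with poor lung reserve enter Cohort 1 unchecked. They do not. DLCO must exceed 35% predicted, and "Patients must be assessed to be a suitable candidate for hemithoracic radiation therapy per the treating radiation oncologist". Section 4.4.4.4 requires "Normal Tissue Complication Probability (NTCP) of the lung <25"% and a contralateral lung V20 below 7%, and patients who miss the constraints are removed before radiation. Section 4.3.3 excludes current pneumonitis, past non-infectious pneumonitis that needed steroids, and interstitial lung disease. None of these uses split perfusion, so they do not replace item 3a, but they are not nothing.
- A reader might infer that the toxicity monitoring is compromised. Nothing in Section 7.2 depends on FEV1 or albumin. The boundaries of 3/6 and 6/12 and the 12 patients per cohort stand. Any effect on the observed toxicity count is conjecture.
- A reader might infer variation between sites. Section 4.4.2 places all trial treatment at one institution.

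The risk context is also mixed. Section 4.1 cites high-grade pneumonitis in 7 of 36 patients (20%) in an outside series, but one Grade 3 case among 21 patients who completed IMRT in a joint prospective study. At a baseline FEV1 of 84% predicted, even the ppoFEV1 reading needs only 30/84 = 36% perfusion to the uninvolved lung, so a typical patient would probably be unaffected.

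**Conclusion.** The point holds as a defect in two operative eligibility criteria. Read literally, item 3a is met by every patient (1 ≥ 0.30q for all q ≤ 1). The available alternatives disagree for patients with low reserve, such as one with FEV1 of 40% predicted and 55% perfusion. The albumin limit, as printed, is a factor of 1000 below the same number in g/dL and excludes nobody.

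On the literal text, what is lost is the FEV1/perfusion gate in Cohort 1 and the albumin gate in both cohorts. The rest of the lung screening, the sample size and the stopping rule remain as they are.

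The FEV1 result needs only the formula as printed and a perfusion share of at most 1. The comparison of readings assumes that FEV1 is expressed in percent predicted. How many enrolled patients would be classified differently cannot be derived from the documents.

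**What to change.** Reconcile item 3a with its own formula and with the scan it requires. State which FEV1 quantity is tested (measured or perfusion-adjusted), which reference it is compared with, and whether the values are in litres or percent predicted. One worked example beside the criterion would remove any doubt. Check the albumin unit in Table 1 and correct it so that the limit can exclude a patient. The clinical limits themselves are for the sponsor to set.

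The cost is two lines of eligibility text. Lung function, perfusion and albumin are already measured at screening, so no procedure is added. The downside is small: some patients who are admissible on the literal wording may become ineligible.

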**Additional Inclusion Criteria – Cohort 2**

1. Patients must be assessed to be a suitable candidate for radiation therapy by the treating radiation oncologist. Patients that do not meet the dose constraints outlined below will be removed from the study prior to radiation therapy.
2. Any prior number of prior therapies, including prior immunotherapy, is allowed.

3. Patient has received prior treatment with a platinum-pemetrexed regimen.

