#### **4.3.3 Subject Exclusion Criteria**

The subject must be excluded from participating in the trial if the subject:

1. Is currently participating and receiving study therapy or has participated in a study of an investigational agent and received study therapy or used an investigational device within 4 weeks of the first dose of treatment.
2. Has a diagnosis of immunodeficiency. Note that patients should not receive steroids during Pembrolizumab administration.
3. Has a known history of active TB (Bacillus Tuberculosis)
4. Hypersensitivity to pembrolizumab or any of its excipients.
5. Has had a prior anti-cancer monoclonal antibody (mAb) within 4 weeks prior to study Day 1 or who has not recovered (i.e.,  $\leq$  Grade 1 or at baseline) from adverse events due to agents administered more than 4 weeks earlier.
6. Has had prior chemotherapy, targeted small molecule therapy, or radiation therapy within 2 weeks prior to study Day 1 and who have not recovered adequately from this treatment ( $\leq$ Grade 2 toxicity at the time of enrollment).
7. Has a known additional malignancy that is progressing or requires active treatment. Patients with a stage I-III cancer that has been cured over two years ago are *not* excluded in the study.
8. Has known active central nervous system (CNS) metastases and/or carcinomatous meningitis. Subjects with previously treated brain metastases may participate provided they are stable (without evidence of progression by imaging for at least four weeks prior to the first dose of trial treatment and any neurologic symptoms have returned to baseline), have no evidence of new or enlarging brain metastases, and are not using steroids for at least 7 days prior to trial treatment. This exception does not include carcinomatous meningitis which is excluded regardless of clinical stability.
9. Has active autoimmune disease that has required systemic treatment in the past 2 years (i.e. with use of disease modifying agents, corticosteroids or immunosuppressive drugs). Replacement therapy (eg., thyroxine, insulin, or physiologic corticosteroid replacement therapy for adrenal or pituitary insufficiency, etc.) is not considered a form of systemic treatment.
10. Has a history of (non-infectious) pneumonitis that required steroids or current pneumonitis.

11. Has an active infection requiring systemic therapy.
12. Has known psychiatric or substance abuse disorders that would interfere with cooperation with the requirements of the trial.

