## **Additional Exclusion Criteria – Cohort 1**

1. Has received prior therapy with an anti-PD-1, anti-PD-L1, or anti-PD-L2 agent.

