# Proprietary Information of MD Anderson

2015-0856

Version 23

Page 17

Toxicity	Hold Treatment For Grade	Timing for Restarting Treatment	Discontinue Subject/Off-Study Criteria (“Unacceptable” Toxicities)
Diarrhea/Colitis	2-3	Toxicity resolves to Grade 0-1.	Toxicity does not resolve within 12 weeks of last dose or inability to reduce corticosteroid to 10 mg or less of prednisone or equivalent per day within 12 weeks.
	4	Permanently discontinue	Permanently discontinue/Off-Study
AST, ALT, or Increased Bilirubin	2	Toxicity resolves to Grade 0-1	Toxicity does not resolve within 12 weeks of last dose.
	3-4	Permanently discontinue (see exceptions below) 	Permanently discontinue/Off-Study
Type 1 diabetes mellitus (if new onset) or Hyperglycemia	T1DM or 3-4	Hold pembrolizumab for new onset Type 1 diabetes mellitus or Grade 3-4 hyperglycemia associated with evidence of beta cell failure.	Resume pembrolizumab when patients are clinically and metabolically stable.
Hypophysitis	2-3	Toxicity resolves to Grade 0-1	Toxicity does not resolve within 12 weeks of last dose or inability to reduce corticosteroid to 10 mg or less of prednisone or equivalent per day within 12 weeks.
	4	Permanently discontinue	Permanently discontinue/Off-Study
Hyperthyroidism	3	Toxicity resolves to Grade 0-1	Toxicity does not resolve within 12 weeks of last dose or inability to reduce corticosteroid to 10 mg or less of prednisone or equivalent per day within 12 weeks.
	4	Permanently discontinue	Permanently discontinue/Off-Study
Hypothyroidism	2-4	Therapy with pembrolizumab can be continued while treatment for the thyroid disorder is instituted	Therapy with pembrolizumab can be continued while treatment for the thyroid disorder is instituted.
Infusion Reaction	3-4	Permanently discontinue	Permanently discontinue/Off-Study
Pneumonitis	2	Toxicity resolves to Grade 0-1	Toxicity does not resolve within 12 weeks of last dose or inability to reduce corticosteroid to 10 mg or less of prednisone or equivalent per day within 12 weeks. Recurrent grade 2 pneumonitis requires discontinuation of pembrolizumab.
	3-4	Permanently discontinue	Permanently discontinue/Off-Study
Renal Failure or Nephritis	2	Toxicity resolves to Grade 0-1	Toxicity does not resolve within 12 weeks of last dose or inability to reduce corticosteroid to 10 mg or less of prednisone or equivalent per day within 12 weeks.
	3-4	Permanently discontinue	Permanently discontinue/Off-Study

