**Note: Permanently discontinue for any severe or Grade 3 drug-related AE that recurs or any life-threatening event.**

 For patients with liver metastasis who begin treatment with Grade 2 AST or ALT, if AST or ALT increases by greater than or equal to 50% relative to baseline and lasts for at least 1 week then patients should be discontinued.

 For patients with Grade 3 transaminitis, will recheck liver enzymes in 1-2 weeks and if the toxicity changes to Grade  $\leq 2$ , patients can remain on study.

 Patients with intolerable or persistent Grade 2 drug-related AE may hold study medication at physician discretion. Permanently discontinue study drug for persistent Grade 2 adverse reactions for which treatment with study drug has been held, that do not recover to Grade 0-1 within 12 weeks of the last dose.

Dosing interruptions are permitted in the case of medical / surgical events or logistical reasons not related to study therapy (e.g., elective surgery, unrelated medical events, patient vacation, and/or holidays). Subjects should be placed back on study therapy within 3 weeks of the scheduled interruption, unless otherwise discussed with Merck. The reason for interruption should be documented in the patient's study record.

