#### **6.1.5.5 Second Course Phase (Retreatment Period)**

Subjects who stop pembrolizumab with SD or better may be eligible for up to one year of additional pembrolizumab therapy if they progress within one year after stopping study treatment. This retreatment is termed the Second Course Phase of this study and is only available if the study remains open and the subject meets the following conditions:

- **Either**

- Stopped initial treatment with pembrolizumab after attaining an investigator-determined confirmed CR according to RECIST 1.1, and
  - Was treated for at least 24 weeks with pembrolizumab before discontinuing therapy
  - Received at least two treatments with pembrolizumab beyond the date when the initial CR was declared

**OR**

- Had SD, PR or CR and stopped pembrolizumab treatment after 24 months of study therapy for reasons other than disease progression or intolerance

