**AND**

- Experienced an investigator-determined confirmed radiographic disease progression after stopping their initial treatment with pembrolizumab
- Did not receive any anti-cancer treatment since the last dose of pembrolizumab
- Has a performance status of 0 or 1 on the ECOG Performance Scale
- Demonstrates adequate organ function as detailed in Section 5.1.2

- Female subject of childbearing potential should have a negative serum or urine pregnancy test within 72 hours prior to receiving retreatment with study medication.
- Female subject of childbearing potential should be willing to use 2 methods of birth control or be surgically sterile, or abstain from heterosexual activity for the course of the study through 120 days after the last dose of study medication (Reference Section 5.7.2). Subjects of child bearing potential are those who have not been surgically sterilized or have been free from menses for > 1 year.
- Male subject should agree to use an adequate method of contraception starting with the first dose of study therapy through 120 days after the last dose of study therapy.
- Does not have a history or current evidence of any condition, therapy, or laboratory abnormality that might interfere with the subject's participation for the full duration of the trial or is not in the best interest of the subject to participate, in the opinion of the treating investigator.
- Absence of rapid progression of disease
- Absence of progressive tumor at critical anatomical sites (e.g. cord compression) requiring urgent alternative medical intervention.

Subjects who restart treatment will be retreated at the same dose and dose interval as when they last received pembrolizumab. Treatment will be administered for up to one additional year.

Visit requirements are outlined in Section 6.0 – Trial Flow Chart.

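### Cohort 2 admits prior immunotherapy with no tolerance condition, so a patient recovered from, for example, Grade 4 colitis or Grade 3-4 nephritis on an earlier PD-1/PD-L1 drug is not clearly barred

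*Combined protocol and SAP*

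**What the plan says.** **Entry.** Section 4.3.2, Additional Inclusion Criteria – Cohort 2, item 2: "Any prior number of prior therapies, including prior immunotherapy, is allowed". The checkpoint-inhibitor bar, "Has received prior therapy with an anti-PD-1, anti-PD-L1, or anti-PD-L2 agent", stands under the Cohort 1 additional exclusions. Cohort 2's own exclusions in Section 4.3.3 are planned hemithoracic radiation and earlier extrapleural pneumonectomy; one further exclusion, shared by both cohorts, concerns inherited radiation hypersensitivity.

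**On study.** In Section 4.4.1.2, Table 3 gives "Permanently discontinue/Off-Study" for Grade 4 diarrhea/colitis and for Grade 3-4 renal failure or nephritis, among others. The note below it adds: "Permanently discontinue for any severe or Grade 3 drug-related AE that recurs or any life-threatening event". Footnote 2 makes a liver exception: "For patients with Grade 3 transaminitis, will recheck liver enzymes in 1-2 weeks", and a patient who falls to Grade 2 or less may stay on.

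**Re-treatment.** Section 6.1.5.5 lets some of the trial's own patients restart pembrolizumab later. One route is for those who "stopped pembrolizumab treatment after 24 months of study therapy for reasons other than disease progression or intolerance"; the other follows a confirmed complete response.

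**The concern.** The plan applies two safety standards to the same kind of event. If it happens on study at a no-restart grade, recovery does not reopen dosing. If it happened earlier on another drug of the class, entry looks mainly at whether the patient is well now. Followed as written, the eligibility text could admit a Cohort 2 patient whom the trial's own dosing rules would never re-dose.

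The stake is first of all participant protection. Secondarily, the off-study events in Table 3 are the primary endpoint (Section 4.2.3) and feed the stopping boundary of 3 in 6 or 6 in 12 (Section 7.2). A recurrence in someone with known intolerance of the class would count there, and would be hard to read as evidence about adding pembrolizumab to radiation.

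**Working it through.** The plan states no figure on this point, so the check sets the entry criteria beside the discontinuation rules.

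**Step 1: trace a patient through entry.** Take a Cohort 2 candidate who had Grade 4 colitis or Grade 3-4 nephritis on an earlier PD-1/PD-L1 drug. The patient is now at Grade 1 or less, more than 4 weeks from the last dose, with adequate organ function and no lung disease of the excluded kinds.

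- Exclusion 4 concerns hypersensitivity to pembrolizumab or its excipients. Colitis or nephritis on another drug does not meet it.
- Exclusion 5 requires a 4-week gap from an anti-cancer antibody and bars patients not recovered "from adverse events due to agents administered more than 4 weeks earlier". It tests present status, not worst past grade. The patient passes.
- Exclusion 9 requires autoimmune disease that is active and was treated systemically within 2 years. It does not name immune-related drug events. Whether a resolved event counts is open, and events treated longer ago fall outside it.
- Exclusion 10 is written in terms of history, but covers pneumonitis only. Exclusion 17 covers interstitial lung disease.
- Table 1 measures current organ function. The patient passes.

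No criterion clearly bars this patient.

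**Step 2: count the Table 3 rows.** The table has 10 drug-related rows; the separate radiation row is left out.

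| Row | Grade with no restart | Entry criterion on a past, recovered event |
|---|---|---|
| Diarrhea/colitis | 4 | none express |
| AST, ALT, bilirubin | 3-4, with footnoted exceptions | none express |
| Type 1 diabetes/hyperglycemia | none; may resume | not applicable |
| Hypophysitis | 4 | none express |
| Hyperthyroidism | 4 | none express |
| Hypothyroidism | none; may continue | not applicable |
| Infusion reaction | 3-4 | exclusion 4, in part |
| Pneumonitis | 3-4 | exclusion 10, if steroids were needed |
| Renal failure/nephritis | 3-4 | none express |
| All other drug-related | 4 | none express |

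Rows with a no-restart grade: 10 − 2 = 8. Rows with a full or partial history bar: 1 + 1 = 2. Rows with no express bar after recovery: 8 − 2 = 6. This counts rows of a table; it is not a measure of patients or risk.

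**Step 3: note what Table 3 does not close off.** Resolved Grade 3 colitis, hypophysitis, hyperthyroidism and other drug-related toxicity may restart. The mismatch is therefore confined to events that meet a permanent-discontinuation criterion. Besides the grades above, those criteria include failure to resolve within 12 weeks of the last dose, inability (in most rows) to taper steroids to 10 mg or less of prednisone per day within 12 weeks, recurrence of a severe or Grade 3 event, and recurrent Grade 2 pneumonitis.

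**Step 4: bound the exposure.** Only Cohort 2 is affected, so at most 12 patients. The documents give neither the number with such a history nor a recurrence rate.

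**The case against.** Admitting prior immunotherapy looks deliberate: it is barred in one cohort and expressly allowed in the other, which serves patients with few other options. Existing cover is also real. Section 4.8.1 prescribes steroids for many severe immune events, so an investigator could reasonably use exclusion 9 to turn away recent cases. Clinically significant conditions of the past 10 years and all prior cancer treatment are reviewed (Sections 6.1.1.3 and 6.1.1.5.2), immune events are looked for before each dose (Section 6.2.3.2), and an inappropriate enrolment may be withdrawn (Section 4.10). Cohort 2 also has its own stopping rule, with accrual suspended after 6 patients. The Investigator's Brochure and the guidance on events of clinical interest are not reproduced, so any advice on re-exposure there cannot be judged.

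This stands as far as it goes. But these safeguards are discretionary, record history, or act once an event has appeared; none is a clear entry rule.

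Two stronger readings are tempting. A reader might infer that any severe immune reaction to the class slips through at entry yet would end dosing on study. The documents do not support that: Table 3 lets several resolved Grade 3 events restart, exclusion 10 bars steroid-treated pneumonitis, and exclusion 9 may reach some others. A reader might also infer from Section 6.1.5.5 that the plan already requires tolerance before any re-exposure. It does not. Only the 24-month route names intolerance; for the complete-response route, Section 4.10.1 refers back to the safety parameters in the entry criteria. The condition beginning "Does not have a history or current evidence of any condition, therapy, or laboratory abnormality" is left to the treating investigator's opinion. Those rules govern re-treatment on study and serve only as an analogue.

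**Conclusion.** The gap holds in limited form. A Cohort 2 patient who has recovered from a severe non-pneumonitis immune event on an earlier PD-1/PD-L1 drug is not clearly barred, although the same type and grade of event on study means permanent discontinuation. This is a mismatch of safety standard, not a contradiction, and no stated figure is wrong.

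The conclusion rests on reading exclusion 9 as not clearly reaching resolved drug-induced events. If it were read to reach them, the gap would narrow to events outside its 2-year limit or not treated systemically. The number affected may be zero. A reader might go on to infer a biased toxicity rate or a distorted stopping rule; without a prevalence or recurrence rate, the documents support neither. The point is a cheap improvement that should be made.

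**What to change.** Add one exclusion for Cohort 2, along these lines:

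> Earlier anti-PD-1, anti-PD-L1 or anti-PD-L2 therapy caused an immune-related event or infusion reaction that met a Table 3 permanent-discontinuation or off-study criterion, including its 12-week non-resolution, steroid-taper and recurrence criteria. The following remain eligible: Grade 3 transaminitis that fell to Grade 2 or less on recheck in 1-2 weeks (footnote 2); hypothyroidism controlled on replacement; and type 1 diabetes or hyperglycemia that is clinically and metabolically stable. For the last two, the specific Table 3 row governs over the general note on life-threatening events.

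The closing clause is needed because the general note, read alone, would catch a Grade 4 endocrine event that its own row allows to continue or resume. Tying the exclusion to the Table 3 criteria, not to grade alone, also covers events that were slow to resolve or that recurred.

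Prior immunotherapy otherwise stays allowed, and the stopping rule, data items and tables do not change. The cost is a short amendment, the possible loss of a few patients with few alternatives, and the grading of past events from outside records that may be incomplete.
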